#### **II.B. Selection of Factors and Levels for Prospective Data Collection**

The sampling frame for the prospective FF design includes the full range of TC clusters along with the full range of hospital and community settings and patient subgroups in which these clusters are implemented. Results from the retrospective analysis will be used together with results from the hospital site visits and responses of Organizational TC Implementation Assessment (OTCIA) form to identify which combinations of TC clusters, care settings, and patient subgroups are most important to study in detail. A FF design matrix will be

constructed that lists all TC components and all important organizational, community, and patient characteristics as possible factors and interactions. The organizational, community and patient characteristics to include in the matrix will be based on the retrospective analysis results showing which cluster/setting/patient interactions achieved significant improvements in outcomes. Results from the OTCIA will be used to determine which cells can be dropped from the design matrix altogether (given zero weight) because the specific TC cluster/setting/patient combination does not exist in practice. Other cells will be assigned increased weight because they include clusters that are highly valued by patients and caregivers, or because the retrospective analysis shows that the cell is associated with improved outcomes. From this design matrix, a subset of comparators will be selected that maximize the study's ability to detect unconfounded main effects and interaction effects involving TC components, care settings, and patient subgroups.

Based on our team's existing knowledge of and experience with the organized TC programs and their TC components, we anticipate that it will be necessary to include at least 6 TC clusters in the prospective FF design with approximately 5 hospitals per cluster in order to adequately characterize the existing heterogeneity in TC program implementation, care settings, and patient subgroups (Figure 1). The exact number of clusters and hospitals per cluster will be determined by analysis of the FF design matrix. Surveys will be fielded with a total of 46 hospitals and an average of 300 patients per hospital.

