Using the data from the survey pilot, item analysis and internal consistency reliability tests will be conducted to determine if there are items that should be dropped and/or to identify items that are not operating as expected. Item analysis will consist of examining item frequencies and missing percentages to ensure that there is item variability and low levels of missing data when the item should have been answered. High levels of missing data may signal either an issue with the way the item is worded or an inappropriate topic for the population. On the patient and caregiver surveys, telephone interviewer comments will also be considered to determine if certain items were problematic or unclear for respondents. Internal consistency reliability tests will be conducted on the a priori theoretical constructs of interest within the survey using a threshold of a Cronbach's alpha of at least 0.70 to be considered acceptable. Item grouping and inclusion will be refined based on the small-scale pilot validation results in order to improve reliability and validity of item scales.

After completion of survey validation work from the pilot tests, the survey instruments will be revised prior to the main survey data collection.

The ACHIEVE survey pilot study was conducted from December 6 2016 to April 30, 2017, with **132** completed patient surveys, **38%** overall response rate (42% mail with phone follow up; 30% phone only).

The pilot survey response rates were lower than estimated in original proposal. Literature demonstrates that a multi-wave, mail survey with telephone follow-up yields a better response rate than a phone-only protocol. Further, the addition of an incentive, whether promised or pre-paid, will also improve response rates, compared to a design without any incentive. Of note, we are unable to promise an incentive to hospitalized patients when they are approached about Project ACHIEVE per guidance from CMS. Proposed changes to the data collection protocol for patients:

1. Initial survey packet mailed to all patients, including \$5 cash incentive payment in the envelope

2. Thank You reminder post card (mailed to all)
3. 2nd survey packet mailed to those who do not respond to the first survey
4. Telephone follow-up with those who do not respond to either mail survey

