Before the main survey administration, using pilot survey estimates, we expected to approach and obtain HIPAA authorization from 27,000 patients (45 participating hospitals approaching an estimated average of 20 patients per hospital per week during the 30-week recruitment period), and have 12,150 completed patient survey (a 45% response rate). Since launching the main survey administration in June 2017, several factors have conspired to reduce the expected patient and caregiver recruitment from participating hospitals. Therefore, we propose to reduce the target number of completed patient surveys from 12,000 to 9,000 and extended the recruitment end date from Jan 21, 2018 to April 15, 2018 for adequate sample size to detect the comparative effects of transitional care strategies on important patient outcomes of interest.

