#### **II.F. Analysis of Patient Survey Datasets**

**Psychometric analysis.** Westat will compile patient survey data from the main study, conduct data cleaning, and generate descriptive statistics from the survey results. Psychometric analyses will be conducted to examine items for variability of response, missing percentages, calculate reliability statistics, perform confirmatory factor analysis to examine the factor structure of the measures, and examine inter-correlations of items and composites. Final composite scores will be created and the survey data will then be used to examine the study's aims and hypotheses regarding TC delivery and outcomes.

**Descriptive statistics.** Continuous variables will be summarized with descriptive statistics (n, mean, standard deviation, median, quintiles, and min and max); categorical variables will be described with counts and percentages. All data will be unweighted. For each survey type

(i.e., patient, caregiver, provider), numerical and/or graphical summaries will be provided overall and by subpopulations.

**II.G. Analysis of TC Component Exposure.** Analyses will be conducted using both hospital- and patient/caregiver-level data. Comparisons on outcomes will be made first using TCCs identified by the hospital; additional analyses will use patient/caregiver identified components. Moreover, additional analyses will also use the number and occurrence of specific categories received within a component as a measure of the TCC received. Finally, an additional issue for consideration is that indicators for TCC presence or absence may not be sufficient for identifying TC component “exposure.” It is expected that TCCs in different communities/hospitals will be implemented to varying degrees. Non-uniform implementation may provide a natural experiment where communities/hospitals serve as their own control and the longitudinal effects of the TC component can be investigated. Using process and implementation data collected at Phase 2, segmented regression analysis of interrupted time series data will allow for comparisons and the estimation of effects for different intensities of TC component exposure.

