Although every effort will be made to include the possible combinations of TC components, it is unlikely that all combinations will be present in each subpopulation. Additionally, although many TC component factors will be measured, it is not expected that all of them will impact the outcomes (sparsity of effects). As an alternative to the factorial design utilized in an experiment, fractional factorials may also be utilized, where a large number of factors can be “screened” to detect important factors even in the presence of a small number of hospitals.

As an additional visualization tool, tree-based models (CART and Random Forests) may also be used to identify potential higher-order interactions. Although the primary analysis will be conducted within a subpopulation, exploratory analyses will be used to investigate the interaction of subpopulation characteristics, patient/caregiver characteristics, and TC components on outcomes. The identification of these potential combinations will help inform additional comparative analyses in the presence of a large number of potentially correlated variables.

- **Pooled Analysis**

Based on the statistical power available with a survey response rate of 35 percent, we conclude that the resulting sample size of approximately 9000 patients from 46 hospitals represents the minimum sample required to ensure that the ACHIEVE prospective analysis can detect the comparative effects of transitional care strategies on important patient outcomes of interest. Our power analysis is based on the study’s ability to detect meaningful differences in outcomes across groups of hospitals that implement different combinations of transitional care (TC) components. Results from the ACHIEVE survey pilot test indicate that the patient survey response rate could be as low as 35 percent. To assess the impact of this response rate on statistical power, we conducted a Monte Carlo simulation using data from the ACHIEVE retrospective analysis, which includes Medicare claims data from nearly 400 hospitals and all Medicare patients hospitalized at these facilities

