over five years. This simulation allowed us to assess the likely statistical power of the prospective analysis even though we do not yet know with certainty the distribution of TC components and patients across participating hospitals. This simulation assumes that the distribution of TC components and patients among hospitals recruited for the ACHIEVE prospective study will be consistent with the distributions observed in the larger population of hospitals included in the ACHIEVE retrospective study.

We conducted the simulation as follows: (1) we drew a random sample of 46 hospitals from the nearly 400 hospitals included in the ACHIEVE retrospective data; (2) we drew a random sample of 560 patients from each of the 46 selected hospitals, corresponding with the planned data collection period of 28 weeks and the planned recruitment rate of 20 patients per week at each facility; (3) we drew a random sample of 35 percent of the recruited patients at each hospital, corresponding with the assumed minimum response rate; (4) we used the 5 clusters of TC components identified from the ACHIEVE retrospective analysis to classify hospitals into comparison groups based on which TC components they implemented for their patients; and (5) we used a multivariable logistic regression model to estimate minimum detectable differences (using a 5% significance level) in 30-day all-cause readmission rates across hospitals grouped by TC clusters, while controlling for patient characteristics that may impact readmission (e.g., age, race, sex, comorbidities, and dual eligible status, as well as others), and accounting for patient clustering within hospitals. We used 1000 replications of this simulation to estimate the variances in minimum detectable differences.

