Simulation results indicate that at an average patient response rate of 35 percent, the study will have sufficient power to detect differences in readmission rates of 2.1 to 2.9 percentage-points across the TC clusters at  $p=0.05$ . This level of statistical power will allow the study to detect effect sizes that are somewhat smaller than the effects estimated from prior studies of care transition interventions, such as the 3.6 percentage-point reduction in readmissions observed in Eric Coleman’s care transition intervention trial. Because the ACHIEVE analysis compares outcomes across multiple active treatment groups defined by TC clusters—rather than comparisons between a single treatment group and control group—and because readmission rates have been declining nationally since 2012, it is important for the ACHIEVE study to be powered to detect somewhat smaller effect sizes than those found in previous two-group studies. For this reason, we consider a response rate of 35 percent to be the minimum acceptable response rate for the ACHIEVE prospective study. This would be approximately 9000 patients.

- **Subgroup Analysis**

Several patient subgroups and community settings are of special interest in the ACHIEVE analysis, including patients with multiple comorbidities, dual eligibles, low-literacy populations, and rural communities. It is not possible to estimate minimum sample sizes for subgroup analysis with any reasonable level of precision given the lack of a priori information about how patient covariates and TC clusters

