are distributed within and across these subgroups. Our simulation analyses suggest that the minimum effect sizes we will be able to detect for subgroups could be more than two times larger than the 2.1 to 2.9 percentage points estimated for the pooled analysis as a whole, when using traditional multivariable analysis methods. For this reason, we anticipate using a modified analytical approach that relies on Bayesian estimation methods that borrow statistical power from the full ACHIEVE sample in order to support statistical inferences about subgroup differences. This method has been used successfully in several recent federal studies of similar magnitude and scope, including the 2016 Mathematica Policy Research evaluation of the CMS Comprehensive Primary Care Initiative. The primary limitation of Bayesian estimation with small subgroup sample sizes is that results can be sensitive to incorrect assumptions about the prior probability distributions of the effect sizes. A major strength of the ACHIEVE study is that we can use estimated effects from the ACHIEVE retrospective analysis to specify informative prior probability distributions for the effect sizes to be estimated in the prospective analysis, rather than basing these distributions on uninformed assumptions.

[figure not shown]
- **Limitations of the Simulation Analysis**

Our simulated power analyses use retrospective Medicare claims data from 2013-14 and are based upon relatively limited a priori knowledge about the TC components implemented by individual hospitals and self-reported by hospital staff. In particular, the measures of TC components are hospital-level measures and do not account for within-hospital differences in the implementation of TC components for individual patients. The ACHIEVE prospective study will collect much more detailed, patient-level information about the TC components received by individual patients, as reported by patients and caregivers. These enhanced, patient-level measures of TC exposure will further improve the study's statistical power to detect differences in outcomes attributable to TC components. As such, this power analysis provides conservative, lower-bound estimates of minimum detectable differences.

[figure not shown]

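### Section II.B's 300 patients per hospital does not fit the 9,000-survey minimum, and the power section labels its detectable differences a lower bound when its own argument makes them an upper bound

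*Combined protocol and SAP*

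**What the plan says.** On sample size, II.B states: "Surveys will be fielded with a total of 46 hospitals and an average of 300 patients per hospital". The same paragraph anticipates at least six clusters with about five hospitals each, and leaves the exact numbers to the design matrix.

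The recruitment update at the end of II.D sets out a proposed change: "reduce the target number of completed patient surveys from 12,000 to 9,000 and extended the recruitment end date from Jan 21, 2018". The new end date is April 15, 2018. The Pooled Analysis text in II.G says that "the resulting sample size of approximately 9000 patients from 46 hospitals represents the minimum sample required". Its simulation steps give the basis: "we drew a random sample of 560 patients from each of the 46 selected hospitals", being 20 per week for 28 weeks, of whom 35% are kept as respondents.

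On power, the Pooled Analysis text concludes that "the study will have sufficient power to detect differences in readmission rates of 2.1 to 2.9 percentage-points across the TC clusters". The text on limitations of the simulation explains that exposure was measured at hospital level, argues that patient-level measures will raise power, and concludes that "this power analysis provides conservative, lower-bound estimates of minimum detectable differences". The opening of II.G sets the order of the outcome analyses: "Comparisons on outcomes will be made first using TCCs identified by the hospital; additional analyses will use patient/caregiver identified components".

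**The concern.** The per-hospital figure in II.B and the one behind the minimum sample describe the same 46 hospitals and cannot both be right. A reader who multiplies out II.B gets a total that cannot be reconciled with the target, and a site-level tracker built on 300 would not measure progress towards 9,000.

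The bound matters because 9,000 surveys and the 35% response floor are defended by the detectable difference lying below the plan's 3.6-point benchmark. A lower bound on a detectable difference says that the real one may be larger, which is the opposite of a safety margin. A reader who instead takes the word *conservative* at face value will credit every analysis with spare power, although the argument offered covers only some of them.

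**Working it through.** **Inputs.** Hospitals: 46 (II.B and Pooled Analysis). Patients per hospital: 300 (II.B); 560 (simulation). Response rates: 30% phone only, 42% mail with phone follow-up and 38% overall (pilot, II.D); 45% (pre-launch expectation, II.D); 35% (Pooled Analysis). Targets: 12,000, reduced to 9,000 (II.D).

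**1. Reproduce the plan's minimum.**
- Recruited per hospital: 20 × 28 = 560.
- Recruited in total: 46 × 560 = 25,760.
- Completed in total: 25,760 × 0.35 = 9,016, or 560 × 0.35 = 196 per hospital.

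This agrees with the stated figure of about 9,000.

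**2. Read 300 as surveys fielded.** The total is 46 × 300 = 13,800.

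| Response rate | Completes from 13,800 | Share of 9,000 |
|---|---|---|
| 30% | 4,140 | 46% |
| 35% | 4,830 | 54% |
| 38% | 5,244 | 58% |
| 42% | 5,796 | 64% |
| 45% | 6,210 | 69% |

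The rate needed is 9,000 / 13,800 = 65.2%. The highest rate anywhere in the document is 45%.

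**3. Read 300 as completes.** The total is 13,800, which is 13,800 / 9,016 = 1.53 times the simulated number and also exceeds 12,000. From 560 recruits it would need 300 / 560 = 53.6% to respond, again above every stated rate. The pre-launch plan does not give 300 either: 27,000 × 0.45 = 12,150, and 12,150 / 45 hospitals = 270.

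**4. Where 300 does fit.** Six clusters × 5 hospitals = 30 hospitals, and 30 × 300 = 9,000. The figure may therefore be left over from a 30-hospital plan. The document does not say so, and the sentence itself says 46.

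**5. Direction of the bound.** At a fixed significance level and power, the minimum detectable difference is proportional to the standard error of the effect estimate, so a gain in power makes it smaller. Write D for the simulated value with hospital-level exposure (2.1 to 2.9 points).
- Patient-reported exposure: if power rises as the plan argues, the detectable difference is at most D. D is then an upper bound.
- Hospital-identified components: this is the kind of exposure that was simulated, so the argument gives no improvement. D is simply the estimate, with no margin from this source.

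Neither case makes D a lower bound.

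**The case against.** The strongest reply is that both faults are editorial. The 9,000 target is stated consistently in II.D and twice in the Pooled Analysis text, nothing derives it from 300, and recruitment was already running against the revised target and end date. Read as completes, 300 overshoots 9,000 and threatens no shortfall. As for the bound, the preceding sentence makes the intent plain; the authors probably meant a lower bound on power. The word *first* in II.G gives an order and does not name a primary analysis, while the introduction to section II stresses measures taken from patients.

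Much of this stands. The 300 is unlikely by itself to cut recruitment short, and a reader should not infer that the study was heading for 4,830 surveys. The hospital-identified comparisons need not be primary for the point to hold: they are planned outcome comparisons, and the stated margin does not reach them. What does not stand is that the text can be left alone. II.B is current text with a sample-size figure that fails on either reading, and the bound is attached to detectable differences, where it reverses the plan's own reasoning.

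A reader might go further and infer that the 2.1 to 2.9 points are overstated, because the readable text gives neither a power level nor a named contrast. The documents do not support that. Figures next to this material are not shown and may hold the details, and nothing says that the band is only a significance threshold. The simulation's five clusters against the six or more anticipated in II.B is not a contradiction either, since II.B leaves the number open. Nor can a weekly recruitment pace be derived for the extended period without assuming that every hospital recruits throughout, which II.D does not state.

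**Conclusion.** Both statements are wrong as written and should be corrected. The 300 per hospital implies 13,800, against 25,760 recruited and 9,016 completed in the power simulation. As surveys fielded it supplies 54% of the target at the plan's 35% response and 69% at 45%; as completes it is 53% too high. This rests only on figures in the document.

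The detectable differences carry the wrong bound: taking the plan's power argument at its word, 2.1 to 2.9 points is an upper bound for the patient-reported exposure analyses and no bound at all for the hospital-identified ones. Whether patient-level measurement will in fact raise power was not tested here. The 9,000 target and the 2.1 to 2.9 figure itself are not shown to be wrong.

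**What to change.** In II.B, replace 300 with an average of about 560 patients recruited and about 196 surveys completed per hospital at 35% response, and say that these give the 9,000 target over 46 hospitals. If 300 was meant as some other quantity, define it and reconcile it with these numbers.

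In the text on limitations of the simulation, change the bound to an upper bound or delete it, and confine the claim of conservatism to the analyses that use patient-reported exposure. Add that the hospital-identified comparisons have the simulated detectable difference with no margin from this source.

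The cost is a few sentences, with no new simulation and no change to the target. The one downside is a slightly less favourable description of the study's power.

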### **II.C. Study Outcome Measures**

***Patient utilization of health services*** include 30-day ED visits, 30-day rehospitalizations

### **II.D. Development and Validation of the Patient Survey Instruments**

Westat will develop a draft survey instruments consisting of items designed to elicit patient experiences with the delivery and receipt of TC components, as well as patient-reported outcomes relevant to transitions in care.

Draft items will be derived from TC measurement constructs identified from an updated literature review, existing validated instruments such as the Coleman CAHPS Care Transition questions, items listed in the NIH PROMIS repository, and constructs elicited from focus groups and hospital site visits. Draft instruments will be refined based on at least two cycles of iterative review by members of the ACHIEVE study team, including members with relevant clinical expertise, TC program development and implementation expertise, and patient and caregiver experience.

Once draft items have been developed, cognitive interviews will be conducted to examine item clarity, comprehension, difficulty, and face validity. Cognitive interviews will be conducted with up to 14 participants in two iterative rounds. The patient survey will also be translated into Spanish and up to 6 cognitive interviews will be conducted to pretest the translated items. The surveys will be revised as needed based on feedback from the cognitive interviews, in preparation for pilot testing.

Significant changes were required in the administration of the patient and caregiver survey component of Project ACHIEVE based on uncovering potential conflict with CMS HCAHPS. Numerous follow-up conversations with CMS, HSAG, PCORI and the ACHIEVE research team yielded agreement on Project ACHIEVE being allowed to field its patient survey 51 days after patient hospital discharge; after most patients contacted for HCAHPS have completed their survey and without causing significant disruption to hospitals' participation in HCAHPS. Of note, we originally proposed to call patients between 30 and 45 days post discharge.

Using the data from the survey pilot, item analysis and internal consistency reliability tests will be conducted to determine if there are items that should be dropped and/or to identify items that are not operating as expected. Item analysis will consist of examining item frequencies and missing percentages to ensure that there is item variability and low levels of missing data when the item should have been answered. High levels of missing data may signal either an issue with the way the item is worded or an inappropriate topic for the population. On the patient and caregiver surveys, telephone interviewer comments will also be considered to determine if certain items were problematic or unclear for respondents. Internal consistency reliability tests will be conducted on the a priori theoretical constructs of interest within the survey using a threshold of a Cronbach's alpha of at least 0.70 to be considered acceptable. Item grouping and inclusion will be refined based on the small-scale pilot validation results in order to improve reliability and validity of item scales.

After completion of survey validation work from the pilot tests, the survey instruments will be revised prior to the main survey data collection.

The ACHIEVE survey pilot study was conducted from December 6 2016 to April 30, 2017, with **132** completed patient surveys, **38%** overall response rate (42% mail with phone follow up; 30% phone only).

The pilot survey response rates were lower than estimated in original proposal. Literature demonstrates that a multi-wave, mail survey with telephone follow-up yields a better response rate than a phone-only protocol. Further, the addition of an incentive, whether promised or pre-paid, will also improve response rates, compared to a design without any incentive. Of note, we are unable to promise an incentive to hospitalized patients when they are approached about Project ACHIEVE per guidance from CMS. Proposed changes to the data collection protocol for patients:

1. Initial survey packet mailed to all patients, including \$5 cash incentive payment in the envelope

2. Thank You reminder post card (mailed to all)
3. 2nd survey packet mailed to those who do not respond to the first survey
4. Telephone follow-up with those who do not respond to either mail survey

Before the main survey administration, using pilot survey estimates, we expected to approach and obtain HIPAA authorization from 27,000 patients (45 participating hospitals approaching an estimated average of 20 patients per hospital per week during the 30-week recruitment period), and have 12,150 completed patient survey (a 45% response rate). Since launching the main survey administration in June 2017, several factors have conspired to reduce the expected patient and caregiver recruitment from participating hospitals. Therefore, we propose to reduce the target number of completed patient surveys from 12,000 to 9,000 and extended the recruitment end date from Jan 21, 2018 to April 15, 2018 for adequate sample size to detect the comparative effects of transitional care strategies on important patient outcomes of interest.

